20.3 Statistical Methods

20.3.1 Primary Outcome Measures and Analysis:

The primary outcome measure is uptake of cervical cancer screening. The results will be reported through summary statistics of the number of participants in each group subsequently engaging or seeking out cervical cancer screening either through services offered after workshop education or self-reported desire to follow up through their community health care provider. Comparisons between the study arms will be based on a binomial test. The analysis will indicate if participants offered additional self-collection education would be more willing to engage in cervical cancer screening. Summary statistics will also include uptake of screening differentiated by reported ethnicity.

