2. STUDY OBJECTIVES AND ENDPOINTS

Objectives	Endpoints

Primary
 
 To evaluate whether educational workshops paired with self-collected hrHPV screening will increase participation in cervical cancer screening among Southeast Asian (Hmong, Burmese, Karen, and Karen) refugee and immigrant populations in Wisconsin compared with offering clinician-collected screening. 	
 Uptake of cervical cancer screening using a self-collect device vs. clinician-based screening.

Secondary
 
 To evaluate participant satisfaction with the educational workshops using satisfaction surveys. To evaluate participant willingness to use self-collection as method for screening. 	
 Participant satisfaction as determined using qualitative methods. General willingness to use a HPV self-collect device at home and/or as the preferred collection method for cervical cancer screening, assessed via mixed methods survey.

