Participants will not be told the full procedures prior to enrollment due to the need to test the hypothesis in this study. Participants in the control group are initially only provided educational materials about the standard of care for cervical cancer screening. While self-collection may or may not be known by the workshop participants in the control group, this is not standard of practice nor usually recommended by clinicians. Whereas the intervention group is provided additional materials about self-collection in the core educational material and is offered as a screening option immediately at the end of the workshop. The uptake of cervical cancer screening by workshop participants at the end of the workshop will then be compared between these two groups to determine.

The informed consent process will include contact information for the PI, who can be contacted if participants or potential participants have questions or concerns.. Informed consent forms will be available in written English, Hmong, or Karen for reference only. All participants will have access to the pre-recorded video in their native language for reference.

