9. PROCESS TO DOCUMENT CONSENT IN WRITING

This study requests of waiver of written documentation of consent

- A written script of the information will be provided orally.
- Pre-recorded video of oral script will be available to all participants for future reference.
- Research presents no more than minimal risk of harm to subjects.
- The research involves no procedures for which written consent is normally required outside of the research context.

This consent requests an alteration of the consent process (HRP-410) due to the following criteria:

- The study involves no more than Minimal Risk to the participants based on clinical standard of care.
- The study could not be practically carried out without the alteration. Participants will be blinded to which group they are randomized in order measure participation rates based on which type of screening method they are offered (clinician-collection vs self-collection)
- The alteration will not adversely affect the rights and welfare of the subjects. Participants will be provided the risks of each collection method in detail during the workshops. If a participant declines the type of screening they are offered will then be offered the other screening method.
- Subjects will be provided the additional pertinent information after participation.
- High proportion of participants in this study population have no or low reading or writing literacy in English or the native language.

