We anticipate a total of thirty workshops, fifteen of which will be control and fifteen of which will be intervention, will be planned in total over a sixteen-month period (Table 1). All workshops will have 8 participants recruited due to limited space of the community center, time, and to accommodate physical spacing needs. There will be two workshop sessions per day (one in the morning and one in the afternoon).

Table 1. Planned Number of Hmong and Karen Participants in the Intervention and Control Workshops

Intervention Workshop	1	2	3	4	5	Total
Hmong	8	8	8	8	8	40
Karen	8	8	8	8		36
Karen	8	8	8			24
Burmese	8	8	8			24
Control Workshop						
Hmong	8	8	8	8	8	40
Karen	8	8	8	8		36
Karen	8	8	8			24
Burmese	8	8	8			24

[figure not shown]
After workshop conclusion, participants will be offered same-day on-site cervical cancer screening depending on assignment in the control or intervention group (clinician-collected screening or self-collection screening, respectively). Participants, regardless of engagement in screening, will then complete a post-evaluation workshop survey (consisting of two surveys, see Appendix C).

Due to ethical concerns and our hypothesis that this population is less likely to do cervical cancer screening if offered clinician-collected screening only. Participants in the control workshops who answer “yes” on the survey to the question “If given the option, instead of having a clinician collect the sample, would you want to collect the sample on your own?,” will be subsequently offered self-collection for their screening method. CHWs will provide to these participants a 5-minute 1-on-1 instruction tutorial on self-collection, translated handout, private room to collect a sample, and then samples sent to the laboratory per protocol.

Similarly, participants will be made aware during the education of the self-collection method, that this is not a usual method that is offered in many clinical practices. If a participant were to visit their usual primary care doctor for an exam, a pelvic examination to obtain a clinician-collected cervical swab for HPV testing and pap smear is the usual method which they should anticipate. We are offering self-collection as studies show growing validity of HPV self-sampling, particularly among hard-to-reach populations.¹⁴⁻¹⁸ With this understanding, self-collection will be offered and encouraged although if participants desire clinician-collection instead this is option will also be made available.

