20. STUDY ANALYSIS

20.1 Statistical Hypothesis

Participation in cervical cancer screening will be higher among women in the intervention group as compared to the control group.

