20.2 Sample Size Justification

For this pilot study, we will enroll 250 participants, which is based on the feasibility of the number of workshops possible during the program length, funding, and resources available through MCHH.⁹ Power estimates are based on comparing the rate of participation between the intervention arm (participants offered self-collected hrHPV) and the control arm (participants offered clinician-collected screening). Estimates of screening rates for the Hmong women population (percent that have had a clinician-collected screening in the last 2-3 years) range from 61- 81%. As we do not have estimates for rates for Karen, Karen, Burmese, or Hmong women, we will use these estimates for participation rates in the control arm. The table below shows the detectable participation rates (and differences between proportions) for the intervention arm for different combinations of power (1- β) and values for the control arm from 0.61-0.81, for the hypotheses $H_0: P \leq p_0$ vs. $H_1: P > p_0$, where p_0 is the rate of participation in the control arm, for a sample size of 250 (125/arm), with a one-sided level 0.05 binomial test.

Control Participation Rate	Detectable Participation Rate (Difference)		
	0.80	0.85	0.90
0.61	0.77 (0.16)	0.78 (0.17)	0.79 (0.18)
0.71	0.85 (0.14)	0.86 (0.15)	0.87 (0.16)
0.81	0.93 (0.12)	0.93 (0.12)	0.94 (0.13)

As an example, if there is a participation rate of 0.81 for those offered clinician-collected screening, we will be able to detect a rate of 0.93 (a difference of 0.12) in the participants offered self-collected hrHPV with a one-sided level 0.05 binomial test with a power of 0.85.

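### As section 20.3.1 reads, the primary test counts women who only say they want to follow up elsewhere, so a positive result would not by itself show higher screening participation

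*Combined protocol and SAP*

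**What the plan says.** Section 20.3.1 gives screening uptake as the primary outcome. It then says results will be reported as the number in each group engaging in or seeking screening "either through services offered after workshop education or self-reported desire to follow up through their community health care provider". The next sentence bases the comparison of arms on a binomial test. The one after says the analysis will indicate "if participants offered additional self-collection education would be more willing to engage in cervical cancer screening".

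Other sections describe the comparison without an intention component:

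- Section 2, primary endpoint: "Uptake of cervical cancer screening using a self-collect device vs. clinician-based screening".
- Section 8: "The uptake of cervical cancer screening by workshop participants at the end of the workshop will then be compared between these two groups".
- Section 20.1, hypothesis: "Participation in cervical cancer screening will be higher among women in the intervention group as compared to the control group".
- Section 20.2: the control rates of 0.61 to 0.81 are the "percent that have had a clinician-collected screening in the last 2-3 years", which is screening received.

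Two sections bear on which samples would count. Section 9 states: "If a participant declines the type of screening they are offered will then be offered the other screening method". Section 11 says control women who answer on the survey that they would want to collect their own sample "will be subsequently offered self-collection for their screening method".

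**The concern.** The combined count is the only numerator in 20.3.1 before the test, and the conclusion drawn from the test is about willingness. An analyst following the section would naturally put stated desire into the primary test. Another analyst could defensibly leave it out, and the choice could be made after the data are seen.

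Stated desire is a weak component for three reasons.

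- **It is not verified.** Under section 12, participation ends with contact about test results. Nothing checks whether a woman was later screened elsewhere.
- **It is not defined.** Appendix C has more than one candidate. Section A item 1 asks every woman how likely she is to have a Pap or pelvic exam. A later item asks unscreened women whether they will be screened within a year (Yes, Maybe, No), followed by five options for where. The plan does not say which item or which answers qualify.
- **It is not comparable between arms.** Control women reach the one-year item after giving no clinician sample but before the later self-collection offer (Appendix C, Section C). Intervention women reach it only if screened by neither method (Sections D and G). A control woman can therefore state a desire and then be screened the same day.

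A significant result might then not mean that more women were screened, and a non-significant one might hide a real gain.

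**Working it through.** **Inputs.** From section 20.2: 125 women per arm, one-sided 0.05, control rates 0.61, 0.71 and 0.81, and detectable rates 0.77, 0.85 and 0.93 (the 0.80 power column). The share *f* of unscreened women counted for a stated desire is assumed throughout, because the documents give no value. Independence between women is also assumed, as in section 20.2, although section 11 randomises whole workshops.

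**Reproducing the plan's figure.** The exact power of a one-sided Fisher test for 0.81 versus 0.93 is 0.854, against a stated 0.85. The exact detectable rates at power 0.80/0.85/0.90 are:

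- control 0.61: 0.7625/0.7728/0.7855
- control 0.71: 0.8467/0.8555/0.8662
- control 0.81: 0.9229/0.9294/0.9373

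Rounded up to two decimals, these match all nine cells of the table. The same test is used below.

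**Formula.** With true screening rate *p*, the combined rate is *q* = *p* + (1 − *p*)*f*. The rejection probability is the sum of the binomial probabilities over the one-sided Fisher region (p ≤ 0.05).

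**1. Equal shares in both arms.** The difference becomes (pI − pC)(1 − f). Power:

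| Control vs intervention | f = 0 | f = 0.25 | f = 0.50 | f = 0.75 |
|---|---|---|---|---|
| 0.61 vs 0.77 | 0.837 | 0.682 | 0.478 | 0.234 |
| 0.71 vs 0.85 | 0.820 | 0.675 | 0.469 | 0.229 |
| 0.81 vs 0.93 | 0.854 | 0.717 | 0.511 | 0.227 |

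For example, at f = 0.50 the rates 0.61 and 0.77 become 0.61 + 0.39 × 0.50 = 0.805 and 0.77 + 0.23 × 0.50 = 0.885. The difference halves from 0.16 to 0.08. With no true difference (0.61 in both arms) the rejection rate is 0.040/0.038/0.037/0.030, so false positives are not inflated.

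**2. Higher share in control (0.4 vs 0.2).**

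- 0.61 vs 0.77 becomes 0.766 vs 0.816: power 0.207.
- 0.81 vs 0.93 becomes 0.886 vs 0.944: power 0.405.
- With no true difference, the rejection rate is 0.0008 at 0.61 and 0.0033 at 0.81.

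**3. Higher share in intervention, no true difference in screening.**

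| Shares (control, intervention) | 0.61 in both arms | 0.81 in both arms |
|---|---|---|
| 0.4, 0.5 | 0.150 | 0.084 |
| 0.2, 0.4 | 0.348 | 0.172 |

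**When a true difference is exaggerated.** The combined difference exceeds the true one only if (1 − pI)fI > (1 − pC)fC, that is, fI/fC > (1 − pC)/(1 − pI):

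- 0.61 vs 0.77: 0.39/0.23 = 1.70
- 0.71 vs 0.85: 0.29/0.15 = 1.93
- 0.81 vs 0.93: 0.19/0.07 = 2.71

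**The case against.** The best counter-reading is that the desire wording belongs to the descriptive summary. It sits in the sentence on summary statistics, the test has its own sentence, and the outcome is named simply as uptake. Sections 2, 8, 20.1 and 20.2 all favour a narrow test, and section 2 already lists willingness to use self-collection as a separate secondary endpoint. This has force: the documents are inconsistent rather than uniformly composite. But 20.3.1 never says the test excludes stated desire, and its sentence on willingness points the other way.

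The broad count could also be deliberate. Section 13.1.4 encourages women who decline on-site screening to attend elsewhere, and an outreach pilot may wish to credit that. Even so, the component is unverified and undefined, and it does not match the hypothesis in 20.1.

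The shares above are assumed. No passage indicates that stated desire would be higher in the intervention arm, and with equal shares the harm is lost power only. That stands, so the conclusion does not rest on the size of any one scenario. The past-screening rates in 20.2 are not same-day on-site rates either, so they do not single out the outcome proposed here; the hypothesis and section 8 do so better.

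**Conclusion.** The concern holds. On its natural reading, 20.3.1 tests a combined count of screening and stated desire, which is not the participation hypothesis in 20.1. On the narrow reading, the plan fails to say so. Either way the numerator of the only primary test is unsettled, and this must be fixed before analysis.

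Under the assumed equal shares of 0.25 to 0.75, power for the plan's own alternatives falls from 0.82–0.85 to between 0.72 and 0.23, with no inflation of false positives. Unequal shares can mask a real gain or produce a false one: 8% to 35% rejection with no true difference in the cases shown. The direction is unknown. The survey routing gives a reason for the shares to differ, because the two arms' intention items are put to differently selected women. All figures assume independent women.

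**What to change.** In section 20.3.1:

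- State that the binomial test uses completed same-day on-site screening (sample collected, yes or no) in response to the arm's offer, with all attending women in their randomised arm as the denominator.
- Reword the sentence on willingness to match that outcome.
- Make stated desire to follow up a separate secondary outcome, and name the survey item and the answers that qualify.
- Report samples by method and by whether they came from the arm's initial offer or a later offer of the other method. State that later self-collection by control women is reported separately and not counted in the primary comparison.
- State whether clinician collection in the intervention arm is part of that arm's offer (as section 11 reads) or a later offer (as section 9 reads), and show the comparison both ways.

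Sections 9 and 11 and Appendix C must also be reconciled on when the other method is offered. Section 9 ties it to declining, in either arm; section 11 and Appendix C place it after a survey answer in the control arm.

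The cost is a few sentences and at most one data field. Section 16.2 already lists which screening was done among the REDCap items. The items listed there give the workshop date but not arm or session, and section 11 plans two sessions a day, so confirm that arm and session are recorded. The survey does record workshop type and same-day screening, so both counts can be tabulated by arm from it. It is not linked to study ID, so it cannot be checked against REDCap, and section 15 allows for attendees who do not complete it. It should not be the only source for an all-attendee denominator. The intention items already exist, and section 20.2 needs no change on this account.

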15. WITHDRAWAL OF PARTICIPANTS	20
16. DATA MANAGEMENT AND CONFIDENTIALITY	20
16.1 Project Data Collection	20
16.2 Data Storage and Maintenance	20
16.3 Confidentiality	20
17. Provisions to Protect the Privacy Interests of Participants	21
18. SHARING OF RESULTS	21
19. DATA AND SPECIMEN BANKING	21

20. STUDY ANALYSIS	21
20.1 Statistical Hypothesis	21
20.2 Sample Size Justification	22
20.3 Statistical Methods	22
21. POTENTIAL BENEFITS TO PARTICIPANTS	22
22. RISKS TO PARTICIPANTS	23
23. PROVISIONS TO MONITOR THE DATA TO ENSURE THE SAFETY OF THE PARTICIPANTS	23
24. ECONOMIC BURDEN TO PARTICIPANTS	23
25. RESOURCES AVAILABLE	23
26. MULTI-SITE RESEARCH	24
27. REFERENCES	24
28. APPENDICES	26

STATEMENT OF COMPLIANCE

I confirm that I have read this protocol. I will comply with the IRB-approved protocol, and applicable regulations, guidelines, laws, and institutional policies.

I agree to ensure that all staff members involved in the conduct of this study are informed about their obligations in meeting the above commitment.

Name	Signature	Date
Name	Signature	Date
[name]		08/08/23

[name]
Principal Investigator

SYNOPSIS

Study Title	Community Health Outreach to Increase Cervical Cancer Education and Self-Collection Screening (CHOICES) Program for Southeast Asian Immigrant and Refugee Women in Wisconsin
Brief Summary	The primary purpose of this study is to determine whether educational workshops paired with self-collected high-risk human papillomaviruses (hrHPV) screening will increase participation in cervical cancer screening among Southeast Asian refugee and immigrant populations in Wisconsin compared with offering clinician-collected screening (total sample size: 250 participants). We hypothesize that participation in cervical cancer screening will be higher among women in the intervention group as compared to the control group.
Number of study sites	1
Study Design	Workshops are randomized to either a control or intervention group.
Primary Objective	To evaluate whether educational workshops paired with self-collected hrHPV screening will increase participation in cervical cancer screening among Southeast Asian refugee and immigrant populations in Wisconsin compared with offering clinician-collected screening.
Secondary Objective(s)	To evaluate participant satisfaction with the educational workshops using satisfaction surveys.

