11. STUDY INTERVENTION

This randomized controlled trial will be done in partnership with MCHH. Previous partnership with MCHH and UW-Madison researchers developed cervical cancer educational workshops designed by CHWs to provide innovative mixed-modality education consisting of pictographs, flipcharts, videos, and hands-on models. These workshops to be conducted in Hmong, Karen, and Burmese and Karen languages were tested in mock workshops with Hmong and Karen participants and through a community advisory panel prior to dissemination. This approach caters to the unique culture and communication styles of Southeast Asian immigrant and refugee populations.

All workshops will be conducted by the CHWs on the study team. If the CHW is not fluent in the target language (such as Karen or Burmese), then the CHW will conduct all study activities in English with a translator available to translate all activities.

All participants attending a workshop will be randomized as a group to either a control or intervention group. Workshops in the control group will provide education recommending standard of care (clinician-collected hrHPV testing and cytology screening). Workshops in the intervention group will be offered the same education with additional education on the option of self-collection (HPV testing only) for their screening method. All participants will have the same basic demographic information collected in MCHH's standard intake form with an additional question on current barriers to screening.

Participants will self-select which workshop day they would like to attend depending on their preferred language. Participants can attend any available date a workshop is being offered until filled. Participants will be blinded to knowing which workshops are control or intervention groups. Participants during consent will be made aware there are two different groups and the difference between the intervention and control group is the education provided and screening method offered at the end of the education session. Participants will be provided the full study details at the end of their participation.

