13.1.3.2 UW Health Post-Workshop Satisfaction Survey (UW-PSS)

Additional survey questions will be administered verbally by CHWs and answers recorded in Qualtrics for data collection. Responses will not be linked to the study ID or other identifiable information. Theme of survey questions is below (full survey in Appendix C):

- Comfort with method (either self-collection or clinician-collection)
- How likely would the participant get screening for cervical cancer again?
- If self-collection (or clinician-collection) was an option, would they have preferred this method.

- If not getting screening today, will they go for screening in the near future?
 - o If not why? Where?
- Understanding of instructions (self-collection)

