20.3.2 Secondary Outcome Measures and Analysis

Qualitative survey data will be obtained through pre- and post-workshop surveys to evaluate the impact of the educational workshops.

Further statistical support for this program will be obtained through consultation with statisticians in the UW-Madison SMPH and/or UW Carbone Cancer Center Biostatistics Shared Resource. For quantitative data, differences will be tested with Wilcoxon Rank-Sum tests for continuous or ordinal categorical data, Chi-Squared tests for unordered categorical data, and binomial tests for dichotomous data.

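### Whole workshops are randomised, but the primary test and the power table treat the women as independent

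*Combined protocol and SAP*

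**What the plan says.** The unit of randomisation is the workshop. The Synopsis states "Workshops are randomized to either a control or intervention group", and Section 11 states "All participants attending a workshop will be randomized as a group to either a control or intervention group". Section 11 plans thirty workshops, fifteen per arm, and adds "All workshops will have 8 participants recruited due to limited space of the community center". Table 1 plans 5, 4, 3 and 3 workshops for the four language groups in each arm. The documents do not describe the allocation method or say whether it is stratified by language.

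The unit of analysis is the woman. Section 20.2 gives detectable rates "for a sample size of 250 (125/arm), with a one-sided level 0.05 binomial test". Section 20.3.1 says of the primary outcome: "Comparisons between the study arms will be based on a binomial test". Section 20.3.2 lists Wilcoxon rank-sum tests, chi-squared tests and "binomial tests for dichotomous data", plus a general intention to consult statisticians. None of these sections mentions correlation within workshops.

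**The concern.** A participant-level binomial test uses a standard error that is right only if one woman's decision tells us nothing about her neighbour's. The protocol's own description makes some dependence plausible. Recruitment runs by word of mouth, through families and churches (7.1). Women choose their own workshop day (11). They share one session, sometimes through a translator (11). Those who want screening wait on site for 30 to 60 minutes (12). Friends or relatives may attend together and decide together on the same day.

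With positive correlation, the variance of the arm difference is larger than the binomial variance. The planned test then rejects a true null hypothesis more often than its nominal level implies, and a test that respects the randomisation has less power than the table states. This is the only formal test of the primary endpoint, so a positive result could partly reflect a standard error that is too small.

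**Working it through.** **1. Reproduce the stated power.** Inputs from Section 20.2: 125 per arm, one-sided 0.05, control rates 0.61, 0.71 and 0.81. Fisher's exact test, fully enumerated for independent women, was used to find the smallest two-decimal intervention rate that reaches each target power. It matches all nine cells of the table. For the worked example, 0.81 against 0.93, it gives 0.854 (stated 0.85). The table therefore contains no hidden allowance for clustering.

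**2. Design effect.** With m = 8 women per workshop, DE = 1 + (m − 1) × ICC = 1 + 7 × ICC. The ICC is an assumption throughout.

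| ICC | DE | 125/DE |
|---|---|---|
| 0.02 | 1.14 | 110 |
| 0.05 | 1.35 | 93 |
| 0.10 | 1.70 | 74 |
| 0.20 | 2.40 | 52 |

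**3. Type I error of the planned test.** For an uncorrected z-test the real one-sided error is approximately P(Z > 1.645/√DE). At ICC 0.05 this is P(Z > 1.645/1.162) = P(Z > 1.416) = 7.8%. Beta-binomial simulation (15 workshops of 8 per arm, control rate 0.61, 200,000 replicates) gives:

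| ICC | Fisher | z-test |
|---|---|---|
| 0.02 | 4.8% | 6.1% |
| 0.05 | 6.3% | 7.8% |
| 0.10 | 8.6% | 10.3% |
| 0.20 | 12.6% | 14.4% |

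Fisher's test starts at 3.7% when the ICC is 0 and passes 5% only above an ICC of about 0.025. A workshop-level t-test (28 df) stays at about 5% throughout.

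**4. Power of the workshop-level t-test at the stated detectable rates.**

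| ICC | 0.61 vs 0.77 (stated 0.80) | 0.71 vs 0.85 (stated 0.80) | 0.81 vs 0.93 (stated 0.85) |
|---|---|---|---|
| 0.02 | 0.80 | 0.78 | 0.83 |
| 0.05 | 0.73 | 0.72 | 0.77 |
| 0.10 | 0.65 | 0.64 | 0.69 |
| 0.20 | 0.52 | 0.52 | 0.57 |

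The detectable difference at 80% power with the same test, for ICC 0.02 / 0.05 / 0.10 / 0.20, is 0.161 / 0.174 / 0.192 / 0.223 from 0.61 (stated 0.16) and 0.116 / 0.124 / 0.134 / 0.150 from 0.81 (stated 0.12).

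**5. Role of language.** If Table 1's balance is kept, differences between languages cancel from the arm contrast, and the ICC that matters is the one within language. To check this, language rates of 0.50, 0.60, 0.70 and 0.80 were assumed, with 5, 4, 3 and 3 workshops per arm.

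- Balanced, no other clustering: Fisher 3.2%, z-test 4.4%. There is no inflation.
- Balanced, within-language ICC 0.05 / 0.10 / 0.20: Fisher 5.8 / 8.0 / 11.8%.
- Allocation not restricted by language, no other clustering: Fisher 6.5%, z-test 8.0%.
- Balanced, workshop-level tests: 2.3 to 3.6% without language adjustment; 4.9 to 5.0% with it (linear model on arm and language, 25 df).
- If languages do not differ, adjustment costs almost nothing: power for 0.61 against 0.77 at ICC 0.05 is 0.735 unadjusted and 0.733 adjusted.

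**6. Sample size.** 30 × 8 = 240, which matches the Synopsis sample-size row and Section 25 (80 + 48 + 48 + 64 = 240). The Synopsis summary, Section 4 and Section 20.2 say 250. The printed totals in Table 1 sum to 40 + 36 + 24 + 24 = 124 per arm, or 248, because the row showing four workshops of 8 (4 × 8 = 32) is totalled as 36; this could be a fault of text extraction. The effect is small: under independence the worked example has power 0.837 at 120 per arm and 0.854 at 125.

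**The case against.** The strongest reply is that the harm depends on an ICC nobody has supplied. If the binomial test means Fisher's test, its conservatism absorbs an ICC up to about 0.025, and at 0.02 the workshop-level power for 0.61 against 0.77 is still 0.80. The worked example's pair of rates is also printed under 80% power, which it still meets at ICC 0.02 (0.83). The study calls itself a pilot sized on feasibility, so a corrected power table would not change the number enrolled. Planned language balance removes an obvious source of between-workshop variation, and it makes the unrestricted-allocation scenario less likely.

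Much of this stands. It rules out calling the inflation certain, and it makes the change to 20.2 advisable rather than essential. Language adjustment is also not needed for validity under balance, since the unadjusted workshop test errs on the conservative side.

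It does not rescue the primary test. The plan does not name Fisher's test, and an uncorrected z-test is already at 6.1% at ICC 0.02. Balancing languages does nothing about shared sessions. Pilot status does not excuse a formal one-sided 5% test whose level depends on an unknown quantity, when a test that holds its level whatever the ICC is available at the same sample size.

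**Conclusion.** The concern holds: the primary analysis is wrong as written because it does not respect the randomisation. The direction is known if decisions within a workshop are positively correlated: too many false positives from the planned test, and less power from a valid one. The size is not known. Over an assumed ICC of 0.02 to 0.20, the one-sided error at a control rate of 0.61 runs from 4.8 to 12.6% (Fisher) or 6.1 to 14.4% (z-test), and workshop-level power for the worked example falls from the stated 0.85 to between 0.83 and 0.57. These figures rest on 15 workshops of exactly 8 per arm and a beta-binomial model. The language results also rest on assumed language rates.

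**What to change.** **Section 20.3.1 (must change).** Replace the participant-level test with a workshop-level analysis adjusted for workshop language. Suitable choices are a linear model or permutation test on the 30 workshop proportions, or a mixed or GEE logistic model with a small-sample correction. Name one as primary. State how workshops are allocated, and permute within language only if allocation was in fact stratified that way.

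**Section 20.3.2.** Apply the same principle to between-arm survey comparisons.

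**Section 20.2 (advisable).** Restate the detectable differences for 15 workshops of 8 per arm over a stated ICC range, and reconcile 240 with 250 and with the printed totals of Table 1.

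**Data.** Workshop date is already stored (16.2), but Section 11 says "There will be two workshop sessions per day (one in the morning and one in the afternoon", so the date alone does not identify a workshop. Add a morning/afternoon field to the study record. The primary outcome also counts self-reported desire to follow up, which comes from the survey, and for that survey "Responses will not be linked to the study ID or other identifiable information" (13.1.3.2). A session code on the survey would let those answers be analysed by workshop. It would identify groups of about 8 women, so first check it against the anonymity commitments in 13.1.3.2 and 16.2, which may need amending.

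**Cost.** Wording changes in three subsections, one session field, some extra analysis work, the anonymity check, and less favourable stated detectable differences. No additional participants.
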